The battle of Mosul was characterized by the use of improvised explosive devices, human shields and suicide bombers in an urban setting. It is unclear whether this type of warfare cause more extensive abdominal injuries to civilians than combatants. Understanding of the correlation between the severity of abdominal injuries, type of warfare and population affected is of importance when planning for surgical care in a conflict setting.

Aim

To assess whether civilians obtain more extensive abdominal injuries than combatants in an urban battle characterized by the use of indiscriminate weapons.

Study Design

An observational retrospective cohort study with longitudinal data collection.

All patients admitted with penetrating abdominal injury subjected to an exploratory laparotomy at Emergency Hospital, Erbil, between October 17, 2016 and July 16, 2017 will be included. Differences in demographics, injury mechanism, time since injury, clinical status on arrival, intraoperative findings, postoperative complications and outcome will be analysed.

Primary Objective

Differences in injury mechanism, organs injured, surgical treatment given, postoperative complications and outcome between civilians *and* combatants.

Secondary Objectives

Differences in surgical treatment given, postoperative complications and outcome between patients with prior surgical treatment of their injury *and* patients without prior surgical treatment.

Differences in surgical treatment given, postoperative complications and outcome between patients who receive surgical treatment less than 24 hours from injury *and* patients who receive surgical treatment more than 24 hours from injury will be analysed.

Statistical methods

Differences between groups will be analysed using t-test and regression models.

List of Abbreviations

EH	Emergency Hospital, Erbil, Iraq
Ex-lap	Exploratory laparotomy
ICRC	International Committee of the Red Cross
IED	Improvised Explosive Device
ISg	Islamic State Group
WHO	World Health Organization

List of Definitions

Civilians	Children <16 years, all women and men \geq 50 years.
Combatants	Men 16-50 or combatants by own admission.
Exploratory laparotomy	Surgical incision through the abdominal wall into the abdominal cavity
PATI	Penetrating Abdominal Trauma Index Assess the severity of injury in patients with knife, gunshot or other penetrating wounds to the abdomen (appendix 1).

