Comparison of surgical treatment given, postoperative complications and outcome between patients with prior surgical treatment of their injury *and* patients without prior surgical treatment.

Differences in surgical treatment given, postoperative complications and outcome between patients who receive surgical treatment less than 24 hours from injury *and* patients who receive surgical treatment more than 24 hours from injury will be analysed.

See chapter Data, *patient files*, for detailed primary and secondary measurements.

Investigation Plan

Study Design

A cohort study with retrospective longitudinal data collection using routinely collected clinical data.

Study Period

Consecutive patients presenting at EH between October 17, 2016 and July 16, 2017 that meet eligibility criteria will be included. Patient history information preceding hospital admission will be included.

Study Location

Emergency Hospital, Erbil, Kurdistan Region, Iraq.

Study Duration for Participants

Participants will be followed from admission until discharged from EH.

Study Population

Recruitment Methods

Patients will be included from the surgical ledger at the Surgical Department of EH.

Inclusion Criteria

- All patients treated with ex-lap due to conflict-related penetrating injury presenting at EH between October 17, 2016 and July 31, 2017 will be included.

Exclusion Criteria

- Patients who received treatment several times during the study period will only be counted as one patient.

Information for Patients and Consent

Since this study is based on data from routine care participants will not be informed, nor will consent be asked of participation, as this could introduce bias and confounding factors. There are moreover no risks or potential gains involved for participants. No incentives or inducements will be provided to any participant or staff involved.

Data

Data Sources

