Data was routinely prospectively collected on paper based patient forms in the clinical setting at EH. A *patient database* with consecutive patients treated between October 17, 2016 and July 31, 2017 was created. It is expected that the database will contain a total of 1,800 patients to produce approximately 160 evaluable subjects. Paper based *patient files* will be queried for demographic information, combatant or civilian status, admission dates, discharge dates, whether the injury was conflict-related or not, geographical site for injury, cause and mechanism of injury, prehospital data, medical history, vital signs at hospital admission, anatomical data and details regarding extent of abdominal injury, number and type of surgeries, details on surgery, need for ICU care, in hospital complications, re-admission including cause of re-admission, outcome including death and cause of death. Paper based data will be entered into a computer database using Epidata entry software (The Epidata Association, Odense, Denmark).

Patient Files

- Time of admission (specified)
- Age in years (specified)
- Sex (Male/Female/Unknown)
- Ethnicity (Arabic/Kurdish/Other/Unknown)
- Civilian/Combatant (Iraqi/Peshmerga/ISg/Unknown/Other)
- Time of injury (specified)
- Geographical location where injury occurred (specified)
- War-related injury (Yes/No/Unknown)
- Cause of injury (Bullet/Shell/Mie/IED/Unknown/Other)
- Mechanism of injury (Gunshot/Stab/Blast/Crush/Fragment/Burn/Traffic accident/Unknown/Other)
- Care prior to admission to EH (First Aid/Medical/Surgery/None given/Unknown)
- Provider of care prior to EH (MSF/Aspen/ICRC/Samaritan Purse/DoH/None)
- Mode of transport to EH (Military/Private car/Motorcycle/Ambulance/Unknown)
- Medical history (Healthy/Prior surgery/ Prior medical/Unknown)
- Body temperature (specified in Celsius)
- Heart rate (specified in beats/min)
- Blood pressure (specified in systole/diastole mmHg)
- Pregnant (Yes/No/Unknown)
- Pregnancy status based on (Lab/Question/Status/Unknown)
- Site and extent of abdominal wound (specified)
- Other injuries (Yes/No/Unknown, specified)
- Preoperative haemoglobin (specified in g/dL)
- Preoperative transfusions (Yes/No/Unknown, specified)
- Use of preoperative radiology (Yes/No/Unknown, specified)
- Time and date of procedure (specified)
- Duration of procedure (specified in hours and minute)

- Antibiotics prophylaxis (Yes/No/Unknown, specified)
- Procedure done (appendix 1 for definition of findings)

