- Perioperative complication (Yes/No/Unknown, specified)
- Postoperative antibiotic prophylaxis (Yes/No/Unknown, specified)
- Postoperative infection (Yes/No/Unknown, appendix 3 for definition)
- Other postoperative complication (Yes/No/Unknown, appendix 2 for definition)
- Need of postoperative intensive care (Yes/No/Unknown, specified)
- Postoperative transfusions (Yes/No/Unknown, specified)
- Use of postoperative radiology (Yes/No/Unknown, specified)
- Further surgery done (Yes/No/Unknown, specified)
- Discharge (Yes/No/Unknown, specified)
- Follow-up scheduled (Yes/No/Unknown, specified)
- Re-admission (Yes/No/Unknown, specified)
- Deceased during hospital stay (Yes/No/Unknown, specified)
- Remarks

Statistical Analyses

Sample Size

Due to the nature of the study, the sample size will be a convenience sample of the available cases during the study period. It is expected that approximately 160 subjects will be enrolled.

Statistical Methods

Analysis will be done by as treated. A 5% significance level will be used. The difference in dichotomous, such as postoperative complication (primary outcome), and categorical outcomes with more than two categories will be tested using chi-square or Fisher test. For differences in continuous variables t-test will be used. In order to adjust our analysis for possible confounders and effect modifiers we will then use linear, logistic, ordinal or multinomial regression models, according to the nature of the outcome (continuous, binary, ordinal or nominal) with injury mechanism as the dependent variable and civilian/combatant as the main explanatory variable. Important demographic and injury specific parameters such as geographical location, date, age, sex, and injured organs, will then be included in the model as potential confounders.

Safety and Monitoring

Participant Confidentiality

The use of identification numbers will ensure anonymity in the data analysis. The participant's age, gender and demographic characteristics will be used as identifying features for analysis. The research team will ensure the ethical principles of beneficence, non-maleficence, justice and respect of patients are adhered to throughout the study.

Data Collection and Management

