Appendix 4: Case Report Form

Exploratory laparotomy following penetrating abdominal injuries: a cohort study from a referral hospital in Erbil, Kurdistan region in Iraq

Case Report Form

1 November 2017

FINAL version

Case Report Form (CRF), version 171101, protocol: _____

Patient Data

Patient no

1. Time of admission

 / /

day month year

 :

hours minutes

Unknown

2. Age

 in years

Unknown

3. Sex

Male

Female

Unknown

4. Ethnicity

Arabic

Kurdish

Other

Unknown

If other, specify

5. Civilian/Combatant

Civilian

Combatant

Unknown

If combatant

Iraqi

Peshmerga

IS

Unknown

Other

If other, specify

Investigators signature _____

day month year

Validated by and date: _____

Case Report Form (CRF), version 171101, protocol: _____

Injury Data

Patient no

[figure not shown]
6. Time of injury

hours minutes

day month year

Unknown

7. Geographical location where injury occurred

Unknown

Other

If other, specify location where injury occurred

Investigators signature

day month year

Validated by and date: _____

Case Report Form (CRF), version 171101, protocol: _____

Injury Data continued

Patient no

8. War-related injury

Yes

No

Unknown

9. Cause of injury

(If several causes number in same order as question 20 and 21)

Bullet

Shell

Mine

IED

Unknown

Other

If other, specify

10. Mechanism of injury

(If several number in same order as question 20 and 21)

Gunshot

Stab

Blast

Crush

Fragment

Unknown

Burn

Other

Traffic accident

If other, specify

Investigators signature _____

_____/_____/_____
day month year

Validated by and date: _____

Case Report Form (CRF), version 171101, protocol: _____

Prehospital Care Data

Patient no

11. Care prior to admission to EH

(If several number in chronological order)

First aid

Medical

None given

Unknown

Surgery

If surgery, specify procedure done

day month year

of procedure

12. Provider of care prior to EH

(If several number in chronological order)

MSF

Aspen

ICRC

Unknown

Samaritan Purse

None

Department of Health

Other, specify

Investigators signature

day month year

Validated by and date: _____

Case Report Form (CRF), version 171101, protocol: _____

Prehospital Care Data cont.

Patient no

13. Mode of transport to EH

(If several number in chronological order)

Military

Private car

Motorcycle

Ambulance

Unknown

Other, specify

14. Medical history

Healthy

Unknown

Prior surgery

Prior medical

If prior surgery specify procedure(s)

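### Delay to surgery is analysed as an exposure only by a split at 24 hours, with exactly 24 hours in neither group, although the protocol collects times that would allow a continuous analysis

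*Combined protocol and SAP*

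**What the plan says.** The objective appears in the synopsis (Secondary Objectives) and again under Secondary Measures. One group is "patients who receive surgical treatment less than 24 hours from injury"; the other is "patients who receive surgical treatment more than 24 hours from injury will be analysed". The outcomes are surgical treatment given, postoperative complications and outcome.

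The Patient Files list includes "Time of injury (specified)" and "Time and date of procedure (specified)". In the Case Report Form (Appendix 4), the injury-time item has hours, minutes and a full date, plus an unknown option. For surgery before arrival at Emergency Hospital (EH), the form says "If surgery, specify procedure done", and the text available shows day, month and year only.

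Statistical Methods names chi-square or Fisher tests, t-tests and a family of regressions. The regression it spells out has injury mechanism as the dependent variable and civilian/combatant status as the main explanatory variable. On covariates it says "Important demographic and injury specific parameters such as geographical location, date, age, sex, and injured organs, will then be included in the model". That list is open, and delay is not among its examples. On size, the Sample Size section says: "It is expected that approximately 160 subjects will be enrolled".

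**The concern.** A two-group split treats surgery at 1 hour and at 23 hours as the same exposure, and surgery at 23 and at 25 hours as different exposures. If risk rises smoothly with delay, the comparison cannot show any gradient within the first day or beyond it, and it uses the data less efficiently than a model in time itself. In a cohort of about 160, that could decide whether an association with delay is seen at all.

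The wording also leaves a hole. A delay of exactly 24 hours is neither less than nor more than 24 hours. With exact times this hardly matters. With rounded times it could leave a few patients unclassified, or classified after the fact.

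The comparison also rests on an interval that is not fully defined. The plan does not say whether surgical treatment means the first operation anywhere or the operation at EH. The Background says that EH served mainly as a referral hospital after late December 2016, so the two readings could differ for many patients.

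**Working it through.** **Inputs from the documents.** N is about 160 and the significance level is 5% (taken as two-sided; the plan does not say). There is no power statement, effect size, delay distribution or share of patients on either side of 24 hours, so there is no figure of the plan's own to reproduce.

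**Assumed inputs.** Log delay is normal, its effect on the log-odds is linear, and the share p on one side of 24 hours is varied.

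**Step 1: information kept by the split.** Relative efficiency = φ(z_p)² / [p(1−p)], where φ is the standard normal density and z_p the normal quantile.

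- 50/50: 0.3989² / 0.25 = 0.637, so 36% is lost.
- 70/30: 0.3477² / 0.21 = 0.576, so 42% is lost.
- 80/20: 0.2800² / 0.16 = 0.490, so 51% is lost.
- 90/10: 0.1755² / 0.09 = 0.342, so 66% is lost.

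Multiplied by 160, these give effective sizes of about 102, 92, 78 and 55 patients.

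**Step 2: effect on power.** Suppose the continuous analysis has 80% power. The split then has power Φ[(1.96 + 0.842) × √efficiency − 1.96]: 61% at 50/50, 57% at 70/30, 50% at 80/20 and 37% at 90/10.

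**Step 3: simulation with a binary outcome.** Settings: N = 160, SD of log delay 1.0, +0.5 log-odds per log-hour, 35% event rate at the median delay, 1,500 data sets per row. The late share follows from the median as 1 − Φ[ln(24/median)].

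| Median delay | Late share | Linear log-time (1 df) | 3-knot spline (2 df) | 24-hour split |
|---|---|---|---|---|
| 24 h | 50% | 83-84% | 77% | 67% |
| 12 h | 24% | 83-84% | 75% | 59% |
| 8 h | 14% | 83-84% | 75% | 49% |
| 6 h | 8% | 83-84% | 75% | 42% |

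The linear column is the range over all four rows. Simulation error is about 1 percentage point (√[0.42 × 0.58 / 1,500] = 1.3 points in the last cell). The spline pays for its second degree of freedom and still beats the split throughout. The times are simulated without recording error.

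**Step 4: change the assumptions.** With uniform delay, efficiency is 3p(1−p), so the loss runs from 25% (50/50) to 73% (90/10). With exponential delay acting linearly in hours, efficiency is (1−p)c²/p, where p is the share below 24 hours and c = −ln(1−p). The loss is then 35% with 80% of patients below 24 hours and 90% with 10% below.

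If risk instead jumps at 24 hours, the ranking reverses. With steps of 0.95, 1.2 and 1.6 log-odds at 50/50, 80/20 and 90/10, power is 83%, 85% and 81% for the split against 63%, 56% and 42% for a linear term. A spline does no better than about 60-62% where the split has 86%.

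**The case against.** The strongest reply is that the loss is not a property of this plan. The documents give no delay distribution and no effect shape; other reasonable choices move the loss from 25% to 90%, and a true step at 24 hours removes it. That stands, so the size can only be stated conditionally. A reader might infer that the plan certainly discards a third to two thirds of the information. The documents do not support that.

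Three other stronger readings also fail.

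- **Delay is recorded to the minute.** Minutes are visible only for injury time, which may be unknown. The form page for the EH procedure is not in the text available, which is no fault of the plan. Earlier surgery elsewhere shows only a date, so if that surgery ends the interval, even the 24-hour class may be uncertain.
- **Late patients are probably a minority.** Nothing in the documents says which group is larger.
- **Time since injury is otherwise ignored.** The synopsis says: "Differences in demographics, injury mechanism, time since injury, clinical status on arrival, intraoperative findings, postoperative complications and outcome will be analysed". That treats it as one more characteristic on an unstated scale, not as the exposure for complications or outcome, but it is there.

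It is also fair to say that this is one secondary objective in a descriptive convenience sample, that 24 hours is the contrast the investigators chose, and that no conclusion of no effect is planned. This limits the weight of the point. It does not explain why the cut is at 24 hours, and it does not close the gap at exactly 24 hours.

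**Conclusion.** The point holds in a limited form. As written, the only analysis of delay as an exposure is the 24-hour split, no reason is given for the cut, and exactly 24 hours belongs to neither group.

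Under a smooth log-linear effect the split is materially weaker. The loss is about 36% to 66% of the information when 10% to 50% of patients are on the smaller side. In the simulated settings its power is about 67% falling to about 40%, against 75-77% for a spline and 83-84% for a linear term. All of this rests on assumed distribution, effect shape, effect size and late share, and recording error could reduce the gain. Under a true step at 24 hours the split is preferable, so the case is for adding a continuous analysis, not for dropping the 24-hour comparison. The point is worth acting on because the repair is cheap; it does not threaten the study as a whole.

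**What to change.** 1. State which operation ends the interval: the first anywhere, or the one at EH. This comes first, because otherwise either analysis models an undefined exposure.
2. State how unknown injury times and date-only operation times are handled, including patients whose 24-hour class cannot be determined.
3. Add injury-to-surgery time in log hours as an exposure analysis for postoperative complications and, if the number of events allows, for death. Choose a linear term or a 3-knot restricted cubic spline before the data are examined.
4. Keep the 24-hour comparison, reported with its effect estimate and confidence interval, and word it so that one group includes exactly 24 hours. Give the reason for the cut if there is one.

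The cost is a few sentences in Secondary Measures and Statistical Methods and a little more analysis; no new data are needed. The downsides are a curve to report beside the 2×2 table, and reliance on reported injury times that may be imprecise.

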Appendix 3 for
definition

Affecting the skin and subcutaneous tissue

day month year

Date of diagnosis

Affecting the fascial and muscle layers

Date of diagnosis

Affecting abdominal cavity

Date of diagnosis

Sepsis

Date of diagnosis

Measures taken (for ex. intensive care, iv antibiotics, dialysis)

Unspecified infection

Date of diagnosis

Explain and measures taken

Investigators signature

_____/_____/_____
day month year

Validated by and date: _____

Case Report Form (CRF), version 171101, protocol: _____

Postoperative Data cont.

Patient no

32. Other postoperative complication

No

Unknown

Appendix 2
for definiton

Yes

 / /

Date of diagnosis

day month year

Type and measures taken

33. Need of postoperative intensive care

No

Unknown

 / /

Yes

Date

If yes, specify reason(s) for intensive care

Discharged from Intensive Care Unit

 / /

Date

34. Postoperative transfusions

None given

Unknown

Units of whole blood

Units of packed red blood cells

Units of Platelets

Units of Plasma

35. Use of postoperative radiology

No

Unknown

CT

X-ray

If use of radiology, specify findings

Investigators signature

_____ / _____ / _____

day month year

Validated by and date: _____

Case Report Form (CRF), version 171101, protocol: _____

Postoperative Data cont.

Patient no

36. Further surgery done

No

Unknown

1. Yes

Date

1.

If yes, specify procedure done

Date

2. Yes

2.

If yes, specify procedure done

Date

3. Yes

3.

If yes, specify procedure done

Investigators signature

day month year

Validated by and date: _____

Case Report Form (CRF), version 171101, protocol: _____

Postoperative Data cont.

Patient no

37. Discharge

No

Unknown

Date of discharge

day month year

Discharged Status

Hospital care complete

Left Against Medical Advice

Unknown

Transferred for further care

Transferred to where

Type of care planned

Investigators signature

_____ / /
day month year

Validated by and date: _____

Case Report Form (CRF), version 171101, protocol: _____

Postoperative Data cont.

Patient no

38. Follow-up scheduled

No

Yes

Unknown

When and reason for follow-up

39. Re-admission

No

Yes

Unknown

Date of re-admission

day month year

Reason for re-admission

40. Deceased during hospital stay

No

Yes

Unknown

Cause of death

Unknown

Date of death

day month year

Investigators signature

_____ / /

day month year

Validated by and date: _____

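### The <24 h versus >24 h surgery contrast carries survivor selection that, taken alone, favours delay on mortality, and the planned analysis does not handle it

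*Combined protocol and SAP*

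**What the plan says.** **The contrast.** Secondary Measures (and Secondary Objectives in the synopsis) compare surgical treatment, postoperative complications and outcome between "patients who receive surgical treatment less than 24 hours from injury" and a late group, defined in the words "patients who receive surgical treatment more than 24 hours from injury will be analysed". Neither place says whether the operation that counts is the first one anywhere or the laparotomy at EH.

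**Entry.** The synopsis takes "All patients admitted with penetrating abdominal injury subjected to an exploratory laparotomy at Emergency Hospital, Erbil". The Inclusion Criteria take "All patients treated with ex-lap due to conflict-related penetrating injury presenting at EH". Recruitment Methods add: "Patients will be included from the surgical ledger at the Surgical Department of EH". Patients already operated on elsewhere are included, since another secondary measure compares them with the rest and CRF item 11 records that surgery.

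**Follow-up and death.** Under Study Duration for Participants: "Participants will be followed from admission until discharged from EH". Death is recorded as "Deceased during hospital stay" (Patient Files list and CRF item 40).

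**Analysis.** Under Statistical Methods, differences in dichotomous and categorical outcomes "will be tested using chi-square or Fisher test". The adjusted models are described only with civilian/combatant status as the main explanatory variable. No time origin, landmark or delayed-entry method is given for the 24-hour contrast.

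**Setting.** The Background places Erbil 94 km from Mosul and describes EH as mainly a referral hospital from late December 2016.

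**The concern.** The groups are defined by something that happens after injury. To be classed as late, a patient must first survive 24 hours from injury, and longer if the operation came later still. A patient classed as early may die on the table or within hours and still count. Patients who would have been operated on late but died while waiting or in transit are never in the ledger.

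A comparison of plain death proportions therefore includes first-day deaths in one group and excludes them from the other. Adding covariates does not put the missing patients back. A true harm of delay could be partly masked, and a reader could take a lower late mortality as reassurance about delay.

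**Working it through.** The plan gives no figure to reproduce for this contrast. The sample of about 160 is a convenience sample with no power statement. The defect is structural, so its size can only be shown under assumptions.

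**1. Size with no true effect of timing.** Assumptions, not in the documents: mortality after 24 hours is 8% in both groups, and a share e of the early group dies within 24 hours of injury. Then early mortality = e + (1 − e) × 0.08, and late mortality = 0.08.

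| e | Early mortality | Late | Odds ratio, early vs late |
|---|---|---|---|
| 2% | 0.02 + 0.98 × 0.08 = 9.8% | 8% | 1.26 |
| 5% | 0.05 + 0.95 × 0.08 = 12.6% | 8% | 1.66 |
| 10% | 0.10 + 0.90 × 0.08 = 17.2% | 8% | 2.39 |

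For e = 5%, the odds ratio is (0.126/0.874) / (0.08/0.92) = 1.66. Values above 1 make delay look better.

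**2. The same question anchored to Table 1.** Let m be early-group mortality, taken from the range in Table 1 (7.4% to 33.3%), and f the assumed share of those deaths that fall within 24 hours. Late mortality, conditional on surviving 24 hours, is m(1 − f)/(1 − mf).

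| m | f = 10% | f = 25% | f = 50% |
|---|---|---|---|
| 7.4% | 6.7% (RR 0.91) | 5.7% (RR 0.76) | 3.8% (RR 0.52) |
| 33.3% | 31.0% (RR 0.93) | 27.2% (RR 0.82) | 20.0% (RR 0.60) |

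RR is late versus early. With 160 patients and 30% or 50% of them late (assumed), the chance of a significant difference from this artefact alone is about 3% to 48% (two-sided 5% assumed). The estimate is more at risk than the test.

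**3. What could cancel it.** If referral leaves the late group with k times the post-24-hour risk, the spurious RR is multiplied by k. It returns to 1 at k = 1/RR, which runs from 1.07 to 1.93 over step 2. Example: m = 10.8% (also in Table 1), f = 25%, k = 1.5 gives RR 1.16, so delay would look worse.

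**4. Dependence on the undefined clock.** Suppose first surgery elsewhere counts, and a share q of the early group reaches EH only after 24 hours. Those patients must also have survived 24 hours, so early mortality becomes (1 − q)m + q × m(1 − f)/(1 − mf). Over m of 7.4% or 33.3% and f of 10% or 50%, q = 75% gives RR 0.81 to 0.98, and q = 100% gives 1.00.

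**5. What a landmark does.** Restricting the early group to 24-hour survivors gives (m − mf)/(1 − mf), the same as the late group, so RR = 1.00 in every scenario of step 2. That assumes late patients are conditioned on 24 hours only. If they are operated on at 72 hours and half of an 8% post-24-hour mortality falls before then (assumed), a 24-hour landmark still shows 8% early against 4/96 = 4.2% late.

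**6. Data.** The Patient Files list has time of injury and time and date of procedure. The CRF shows only day, month and year for death (item 40) and for prior surgery (item 11).

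**The case against.** The contrast is a secondary one, worded as a difference among operated patients. It makes no claim about the effect of delay, and the sentence on staffing and facility planning follows the civilian/combatant hypothesis. This stands: it limits the weight of the point, though not the need to analyse death sensibly once it is compared.

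Four stronger readings are tempting, and the documents do not support them.

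- *Delayed surgery will look safer than it is.* EH was mainly a referral hospital from late December 2016, so the late group may be a more complicated case mix. Step 3 shows that a modest excess risk offsets the selection. The documents give no figures to settle the net direction.
- *The bias is present whichever operation stops the clock.* If first surgery elsewhere counts, early patients must also survive to a laparotomy at EH, so some of their early deaths are missing too. Step 4 shows the asymmetry shrinking and, at the limit, disappearing.
- *This is immortal-time bias.* Follow-up starts at admission and both groups must survive to laparotomy. Survivor selection, or left truncation, is the accurate term. It would become immortal time only if risk were counted from injury.
- *The early group loses complications.* Complications are graded by Clavien-Dindo (Appendix 2), where Grade V is death, so an early postoperative death is itself a complication. The argument fits only non-fatal events such as surgical site infection.

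It is also fair that the assumed e of 2% to 10% has no support in the documents. With half of 160 in the early group (assumed), e = 2% is 0.02 × 80 = 1.6 deaths.

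**Conclusion.** The point holds as a structural one. By definition, nobody classed as late can have died in the first 24 hours after injury, while the early group can include such deaths. The planned tests do not deal with this, and the regression is specified for another exposure. Taken alone, the selection tilts the mortality comparison towards delay: odds ratio 1.26 to 2.39 under the assumptions of step 1, or a late/early risk ratio of 0.52 to 0.93 under those of step 2. These figures show plausible size and do not forecast the result. The net direction is unknown, and the bias may be small or absent depending on which operation counts and when early patients reached EH. The contrast should be corrected before analysis, because most of the data needed are already planned for collection.

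**What to change.** 1. State which operation stops the 24-hour clock.
2. For this contrast, analyse death on the time-since-injury scale, with every patient entering the risk set at the EH laparotomy. This includes patients first operated on elsewhere: entering them at that earlier operation would credit them with time in which their death could not have been observed.
3. As a simpler sensitivity analysis, use a landmark that counts only patients alive at that point in both groups, and list earlier deaths separately. Where only the date of death is known, set it at the end of the calendar day after injury, which falls 24 to 48 hours after injury. State that this does not remove selection between the landmark and a later operation (step 5).
4. For non-fatal complications such as surgical site infection, report early death as a competing event.
5. State that the result is an association among patients who survive to laparotomy at EH and does not estimate the effect of delay from injury.

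Cost: a little more analysis and some added wording, with no new CRF fields. A few early deaths leave the landmark contrast and are reported separately. Date-only fields for death and prior surgery make the landmark approximate unless the source notes give times.
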